5.2 REPORTING PROCEDURES

At each data collection (30 days, 90 days and 6 months from the thrombectomy) the investigator will determine whether adverse events about the device and procedure have occurred. Subjects participating in the study should be encouraged to report these AEs spontaneously or in response to general, non-directed questioning.

Relevant events will be collected from the signing of informed consent to the completion of the follow up 6 months post index procedure.

19/10/25; V1.0

Adverse Events

AEs will be recorded for the CAVT and relevant procedure only.

Any AEs related to the CAVT will also be reported to the company Penumbra and MHRA.

Please find in Appendix 3 expected adverse events of CAVT and relevant procedure.

Serious Adverse Events

Death due to any pre-existing conditions will not be reported as SAEs.

Serious adverse events will be recorded.

Only CAVT related SAEs will be reported to the Principle Investigator, the Chief Investigator and Sponsor within 24 hours of being aware of the event. An Independent Medical Reviewer for the SAEs will also be appointed and the opinion will be recorded along with the PI / CI opinion. A SAE form should be completed.

All CAVT related SAEs should be reported to the Name of REC and copied to the Sponsor, and Penumbra where in the opinion of the Chief / Principal Investigator and the Independent Medical Reviewer, the event was:

- 'related', i.e. resulted from the administration of any of the research procedures; and
- 'unexpected', i.e. an event that is not listed in the protocol as an expected occurrence

Reports of related and unexpected SAEs should be submitted within 15 days of the Chief / Principal Investigator becoming aware of the event, using the Non-CTIMP safety report to REC form for non-IMP studies.

Sponsor contact details for reporting SAEs

Please send SAE forms to: R&D Governance / R&D Office

[contact] (Mon to Fri 09.00 – 17.00)

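### Section 5.2 makes a REC report of a CAVT related SAE depend on two concurring opinions and gives no rule for disagreement, so the independent reviewer can remove REC reports but never add one

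*Protocol*

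**What the plan says.** Protocol section 5.2 (Reporting Procedures) sets up two assessments of SAEs: "An Independent Medical Reviewer for the SAEs will also be appointed and the opinion will be recorded along with the PI / CI opinion".

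A CAVT related SAE is then to be reported to the REC, with copies to the Sponsor and Penumbra, "where in the opinion of the Chief / Principal Investigator and the Independent Medical Reviewer, the event was" related and unexpected. Related means that the event "resulted from the administration of any of the research procedures; and" the second criterion must also be met. Unexpected means "an event that is not listed in the protocol as an expected occurrence".

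The next sentence allows 15 days for the report, counted from the Chief / Principal Investigator's awareness. The reviewer is not mentioned there and has no deadline of their own.

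The same section contains three provisions that do not depend on the reviewer:

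- "Serious adverse events will be recorded".
- CAVT related SAEs "will be reported to the Principle Investigator, the Chief Investigator and Sponsor within 24 hours of being aware of the event".
- "Any AEs related to the CAVT will also be reported to the company Penumbra and MHRA".

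**The concern.** A second, independent opinion on an SAE is normally wanted because a treating team may be slow to attribute harm to its own procedure. That purpose is served only if the second opinion can bring an event to attention. With the two opinions joined by 'and', it cannot: if the investigator says no, the reviewer's yes does not satisfy the condition, and if the investigator says yes, the reviewer's no defeats it.

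The section anticipates two separate opinions, since each is recorded, yet it does not say what a site should do when they differ, or when the reviewer has not answered by day 15. What is at stake is the completeness of what the REC sees about related and unexpected device or procedural harm. The morbidity and mortality profile of CAVT is one of the two primary objectives (section 2.1).

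**Working it through.** The protocol gives no figure on this point, so the check is one of wording and logic.

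**Step 1: the four possible outcomes.** Let I be the set of CAVT related SAEs that the investigator holds to be related and unexpected, and R the set that the reviewer so holds.

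| Investigator | Reviewer | As written ('and') | Investigator alone | With 'or' |
|---|---|---|---|---|
| yes | yes | report | report | report |
| yes | no | condition not met | report | report |
| no | yes | condition not met | no report | report |
| no | no | condition not met | no report | no report |

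As written, the reported set is I ∩ R, which is never larger than I. With 'or' it is I ∪ R, which is never smaller than I. Compared with the investigator alone, the present wording changes only row 2, and it does so by removing a report. This needs no assumed rate.

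**Step 2: is there room for disagreement?** Relatedness is a judgement, so yes. Section 5.2 words it in terms of research procedures, while the events concerned are described as CAVT related, which leaves something to interpret. Expectedness is mostly a look-up in a list, but not wholly. Infection and pseudoaneurysm stand in Appendix 3 (expected adverse events) and not in Appendix 4 (expected serious adverse events), and section 5.2 does not say which list governs an SAE. Two assessors could differ on a serious infection.

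**Step 3: which routes depend on agreement?**

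| Route in section 5.2 | Needs the reviewer's agreement? |
|---|---|
| Recording of SAEs | No |
| CAVT related SAE to PI, CI and Sponsor within 24 hours | No |
| CAVT related AE to Penumbra and MHRA | No |
| Report to the REC, with its copies to Sponsor and Penumbra | Yes, read literally |

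The copies are tied to the REC report, but the Sponsor and Penumbra are told of CAVT related events by the other routes.

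**Step 4: illustration of size, on assumptions that are not in the protocol.** Suppose each assessor recognises a truly reportable event with probability s, independently of the other. Then 'and' reports s² of such events and 'or' reports 1 − (1 − s)².

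| s (assumed; equals the investigator-alone share) | 'and' = s² | 'or' = 1 − (1 − s)² |
|---|---|---|
| 0.7 | 0.49 | 0.91 |
| 0.8 | 0.64 | 0.96 |
| 0.9 | 0.81 | 0.99 |

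Independence is unlikely, because both assessors judge the same event and one criterion is largely a list. At the other extreme, if they always agree, 'and' and 'or' both report s and the difference is zero. Under these assumptions the difference between the two rules therefore runs from zero up to 0.91 − 0.49 = 0.42, 0.96 − 0.64 = 0.32 or 0.99 − 0.81 = 0.18 for the three values of s. The protocol does not say where in that range the study would fall.

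**The case against.** The strongest reply is that this is silence on disagreement rather than a stated veto. The protocol never says that a dissent stops a report. It says that "the opinion will be recorded along with the PI / CI opinion", and the 15-day clock runs without reference to the reviewer. That is fair as far as it goes: the block is the consequence of an unmet condition, not an explicit prohibition. But the condition is written with 'and', so a site that follows the text has no ground to submit on one opinion.

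A reader might infer that the rule hides device harm from everyone, or weakens the safety signal of the study as a whole. The document does not support this. As step 3 shows, recording, the 24-hour report and the report to Penumbra and the MHRA stand without the reviewer. Nor does section 2 make the mortality and morbidity objective or the device related SAE objective depend on the REC condition. Nothing links REC reports to the absence of Stop/Go criteria in section 6.2 either; that absence is explained by the observational design.

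It is also said that the rule has little to act on, because Appendix 4 already lists death, haemorrhage, arrhythmia, cardiac injury, myocardial infarction, stroke and others as expected. This stands, and it limits the number of events affected under either wording.

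Finally, the illustration models only missed events and ignores that a second opinion can also correct a false attribution. That stands too. The percentages are not evidence about this trial, and a claim that the reviewer is worse than having none would rest on those assumptions. The direction in step 1 does not.

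**Conclusion.** The point holds for the REC route. As worded, the reviewer can leave the number of REC reports unchanged or lower it, and cannot raise it, and the section gives no rule for disagreement. This is a rule stated in the protocol with an unhelpful result, and it is not a detail that a statistical analysis plan would be expected to supply.

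The size is unknown and probably small. It depends on how often the two assessors would differ, which the protocol does not allow one to estimate, and it is nil if they always agree. The conclusion rests on reading 'and' literally and on an SAE counting as an AE for the Penumbra and MHRA route.

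One limit applies to the remedy as well. The condition covers only SAEs already described as CAVT related, so an event that the site has called unrelated may never reach this step under either wording.

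**What to change.** In section 5.2:

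1. Replace 'and' with 'or' between the Chief / Principal Investigator and the Independent Medical Reviewer, so that either opinion is enough for a REC report.
2. State that neither may downgrade the other's assessment.
3. State that both opinions are included in the report when they differ.
4. State that the 15-day clock does not wait for the reviewer's opinion.

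The cost is a change of one word and a sentence or two in a version 1.0 protocol. The downside is a few more reports to the REC, some of which will later be judged unrelated. No change to data collection, sample size or analysis is needed.

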6 STATISTICS

6.1 THE NUMBER OF PARTICIPANTS

Target sample size is based on recruitment of 12 centres, based on estimates from current PE Response team referrals and previous year thrombectomy numbers. We estimate that each centre will see around 130 eligible patients per year and perform approximately 13 thrombectomies per year (4). Therefore, across the 12 centres we expect to see around 3000 eligible patients and around 300

thrombectomy patients across the two years. We expect around 70% of patients to consent to take part in the study due to its observational nature and therefore we expect between 2000 of PERT referred patients and 200 thrombectomy patients across the two years. These allow for approximately 30% of eligible patients to decline to participate in the study which is higher than the STRIKE PE (8) rate.

The interim analysis of the STRIKE PE (8) study demonstrated a change of LV/RV ratio of (mean reduction of 0.38 (SD \pm 0.27) (P< .001)) at 48 hours, which is equivalent to an effect size of d >1 (Cohen's d). However, the STRIKE PE study was within a European setting and with different thresholds for treatment than current UK based guidelines. We are therefore conservatively anticipating approximately 25% of the thrombectomy group being classified as high risk. Therefore, our patient group, we anticipate a smaller change in LV/RV ratio which is still clinically significant. With a sample size of 200 we would be able to detect a standardised effect size of d=0.2 (Cohen's d) at 90% power with an alpha 0.05. As a key comparison of interest of the high-risk subgroup at 90% power a small effect size will be detectable.

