6.2 ANALYSIS

Patient demographic and clinical characteristics will be summarised using appropriate descriptive statistics. The primary outcome, change in LV/RV ratio before and at 48 hours post baseline will be summarised according to risk group and overall and will be assessed with a two-sided paired t-Test. Linear regression analysis will be used to identify factors, including severity, affecting the change in LV/RV ratio. Survival analysis will be used to model factors affecting mortality. Data will be analysed using R or Stata. An unblinded interim analysis at 100 patients will be performed at 6 month follow up with focus on the primary outcomes. No Stop/Go criteria will be applied as the PE response team decision to treat or not is not protocolised and the study is observational only. A detailed statistical analysis plan will be written with the University of Plymouth Medical Statistics group and finalised before database lock.

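### With 200 patients and the planned two-sided paired t-test, power at d=0.2 is about 80%, not the stated 90%; 90% power is reached at d=0.23

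*Protocol*

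**What the plan says.** Section 6.1 of the protocol derives about 200 consenting thrombectomy patients from 12 centres over two years. It then cites a reference study with a mean reduction in ventricular ratio of 0.38 (SD 0.27), "which is equivalent to an effect size of d >1 (Cohen's d"), and anticipates a smaller change in the UK population. The assurance offered for that smaller change is: "With a sample size of 200 we would be able to detect a standardised effect size of d=0.2", "at 90% power with an alpha 0.05".

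Section 6.2 names the primary analysis. The change from before the procedure to 48 hours "will be assessed with a two-sided paired t-Test".

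The only allowance for loss in section 6.1 concerns consent: "These allow for approximately 30% of eligible patients to decline to participate in the study". It is applied before the figure of 200 is reached.

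**The concern.** Sample size, effect size, alpha, power, test and sidedness are all stated in the protocol, so nothing needed to check the claim is left to the statistical analysis plan. For a paired t-test, 200 pairs at d=0.2 is the familiar 80% power case, not the 90% case.

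The protocol expects a smaller effect than the reference study found and uses this sentence to show that the study can still detect it. A reader on the ethics committee or at the funder would take from it a 10% chance of missing an effect of d=0.2. The design described gives about 20%. Section 4.5 also makes 200 thrombectomies the completion point if recruitment runs fast, so the number has some operational weight.

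**Working it through.** **Inputs**

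- n = 200 pairs, d = 0.2, power 90%, alpha 0.05: section 6.1.
- Two-sided paired t-test: section 6.2.
- Meaning of d: section 6.1 reports a mean change of 0.38 with SD 0.27 as d above 1. Since 0.38 / 0.27 = 1.41, that statement reproduces when d is the mean change divided by the quoted SD. The same convention is used here.

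**Formula.** With df = n − 1 and noncentrality λ = d√n, power = P(T > t₀.₉₇₅) + P(T < −t₀.₉₇₅), where T follows a noncentral t distribution.

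**Step 1: the protocol's own claim.** λ = 0.2 × √200 = 2.83, df = 199, critical value 1.972. Power = **80.4%**. As a check, the normal approximation Φ(2.83 − 1.96) gives 80.7%. The stated 90% is not reproduced; the gap is 9.6 percentage points.

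**Step 2: effect detectable with n = 200.** At 90% power, d = **0.230** (normal approximation: (1.96 + 1.28) / √200 = 0.229). At 80% power, d = 0.199.

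**Step 3: pairs needed for 90% power at d = 0.2.** Exact: **265**. Normal approximation: ((1.96 + 1.28) / 0.2)² ≈ 263.

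**Step 4: other readings that might give 90%**

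| Reading | Power at d = 0.2 | Comment |
|---|---|---|
| One-sided 5%, n = 200 | 88.0% | Contradicts section 6.2; 90% needs 216 |
| Two-sided, n = 210 (70% of 300) | 82.3% | Not the stated n |
| Two-sided, n = 218 (70% of 12 × 13 × 2 = 312) | 83.6% | Not the stated n |
| One-sided 5%, n = 218 | 90.3% | Departs from both the stated n and the stated test |
| Two-sided, n = 300 | 93.2% | Count before consent loss |
| Two groups, 100/100, 200/200 or 50/150 | 29%, 52%, 23% | Not the planned test |
| d divided by the raw SD, n = 200 | 90% only if the pre/post correlation is about 0.62 | No correlation is given |

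**Step 5: size in ratio units (illustrative).** With the reference study's SD of 0.27, d = 0.230 is 0.230 × 0.27 = 0.062 and d = 0.20 is 0.20 × 0.27 = 0.054.

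**Step 6: incomplete pairs.** The protocol gives no rate of missing echocardiograms. If 10% to 20% of the 200 pairs were missing (an assumption):

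| Complete pairs | Power at d = 0.2 | d at 90% power |
|---|---|---|
| 180 | 76.1% | 0.243 |
| 160 | 71.0% | 0.258 |

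**The case against.** The best defence is rounding. The protocol quotes d coarsely, and 0.230 rounds to 0.2; on that reading n, alpha, power and test all agree. This may well be how the sentence arose, as may 80% mistyped as 90%. The protocol does not say so, however, and a reader who takes d=0.2 at face value is given a power about 10 points too high.

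The second argument concerns consequence, and most of it stands. The sample size comes from expected recruitment, not from this calculation. The study is observational with no stop/go rule. The reference effect is about six times the detectable one (1.41 / 0.230 = 6.1). The difference between d=0.20 and d=0.23 is 0.008 in ratio units, and those units rest on another population's SD. No enrolment figure or analysis changes. The protocol also does not name d=0.2 as a minimum important difference, so the error cannot be described as missing a declared target.

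The missing-pairs figures are secondary. The 10% to 20% is assumed. The unrounded recruitment estimate of 218 would leave some margin: about 196 to 175 pairs after the same loss. That margin is not assured, because section 4.5 can end recruitment at 200. The Day 2 echocardiogram window (+2/−1 days) limits loss through early discharge, but section 4.3 admits patients who die within 96 hours, and some of them may have no second measurement.

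**Conclusion.** The concern holds. For the test fixed in section 6.2, 200 complete pairs give 80.4% power at d=0.2, against the stated 90%. The detectable effect at 90% power is d=0.230, and 265 pairs would be needed for the claim as printed. This rests on reading d as mean change over the SD of change, which is how section 6.1 forms its own reference effect, and on all 200 patients having both measurements. No alternative reading that keeps the stated n, test and sidedness yields 90% without an input the protocol does not give. The error lies in a relied-on figure and does not undermine the study's ability to detect an effect near the reference size.

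**What to change.** Replace the power sentence in section 6.1. Suggested wording:

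> With 200 complete pairs of baseline and 48-hour echocardiographic ratios, a two-sided paired t-test at the 5% level has 90% power to detect a standardised mean change of d=0.23 (80% power for d=0.20), where d is the mean change divided by the standard deviation of the change.

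If the sponsor is willing to state an expected rate of missing pairs, add a clause such as: if 10% to 20% of pairs are missing, the detectable d at 90% power is 0.24 to 0.26. That clause is optional and should carry the sponsor's own assumed rate.

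If 90% power at d=0.20 is truly required, the target becomes 265 complete pairs. That would be a change of recruitment plan, and nothing in this finding calls for it.

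The cost is one sentence. Enrolment and analysis stay as they are, and the stated figure becomes slightly less favourable.

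### About 50 high-risk patients give 90% power only for d of about 0.47 within the subgroup, or 0.53 against intermediate risk, not for the small effect that section 6.1 claims

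*Protocol*

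**What the plan says.** Protocol section 6.1 plans 200 thrombectomy patients and anticipates "approximately 25% of the thrombectomy group being classified as high risk". For the whole group it states: "With a sample size of 200 we would be able to detect a standardised effect size of d=0.2", on Cohen's scale, "at 90% power with an alpha 0.05". The next sentence turns to the subgroup: "As a key comparison of interest of the high-risk subgroup at 90% power a small effect size will be detectable". It gives no subgroup size, no value of d and no comparator.

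Section 6.2 says that the change in ventricular ratio "will be summarised according to risk group and overall" and "will be assessed with a two-sided paired t-Test". It also plans a linear regression of the change, with severity among the factors. Secondary objective 4 concerns effectiveness and risk in high-risk patients. Objective 7 concerns the relation between severity and outcome.

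**The concern.** The paragraph sets d=0.2 as the effect detectable with 200 patients, then claims a small effect at the same power for a quarter of them. The detectable effect grows with one over the square root of the sample size, so a group of one quarter has roughly twice the detectable effect. A comparison of that quarter with the rest does worse still. The two sentences cannot both describe an effect of about the same size.

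The protocol calls this a key comparison. A reader who relies on 90% power for a small effect could take a non-significant difference between high and intermediate risk as evidence that there is none. The study would in fact often miss a difference of that size.

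**Working it through.** **Inputs**
- Thrombectomy patients: 200 (section 6.1).
- High-risk share: 25%, so 0.25 × 200 = 50 high risk and 150 intermediate risk.
- Power 90%, alpha 0.05 (section 6.1); two-sided paired t-test (section 6.2).
- Cited study: mean reduction 0.38, SD 0.27 (section 6.1), so d = 0.38/0.27 = 1.41.
- Assumed: all 50 patients have paired ratios, and the SD of the change is 0.27 in both risk groups.

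**The plan's own figure, n = 200**

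Normal approximation: detectable d = (1.960 + 1.282)/√200 = 0.229; the noncentral t gives 0.230. Power at d=0.2 is 80.4%, and 90% power at d=0.2 needs 265 patients. So 0.2 is obtained only by rounding down from 0.23, or roughly by a one-sided test (88% power), which section 6.2 does not use.

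**Within the high-risk subgroup, 50 pairs**

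d = (1.960 + 1.282)/√50 = 0.458; the noncentral t with 49 degrees of freedom gives **0.468**. At SD 0.27 that is 0.468 × 0.27 = 0.126 ratio units. Power at d=0.2 (0.054 units) is **28%**. For 90% power at d=0.2, 265 high-risk patients are needed. At a 25% share that is 265/0.25 = 1,060 thrombectomies.

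**High versus intermediate risk, 50 v 150, unadjusted**

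d = (1.960 + 1.282) × √(1/50 + 1/150) = 3.242 × 0.1633 = 0.529; the noncentral t gives **0.532**, or 0.532 × 0.27 = 0.144 ratio units. Power at d=0.2 is **23%**.

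**Do other settings rescue the sentence?**

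| Setting | Within | High v intermediate |
|---|---|---|
| Two-sided, 90% power | 0.47 | 0.53 |
| One-sided, 90% power | 0.42 | 0.48 |
| Two-sided, 80% power | 0.40 | 0.46 |
| 75 high risk (25% of 300), two-sided, 90% | 0.38 | 0.43 |

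None comes near 0.2. Missing echocardiograms make it worse: 40 pairs give d=0.53 within the subgroup, and 35 give 0.56.

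**Precision at SD 0.27**

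Half-width of the 95% interval within the subgroup: 2.01 × 0.27/√50 = 0.077. For the contrast: 1.97 × 0.27 × 0.1633 = 0.087.

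**The case against.** **Small is not defined.** The protocol attaches d=0.2 to the 200 patients, not to the subgroup. Cohen's labels are sometimes read as bands, with small running from 0.2 to just under 0.5; on that reading 0.47 would qualify. A reader might infer that the protocol claims 90% power for d=0.2 in high-risk patients, but it does not say so in words. The 28% and 23% are therefore conditional on that reading. The band reading is strained, though, directly after a sentence that uses d=0.2, and it does not cover the unadjusted contrast at 0.53.

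**Covariate adjustment could help.** Section 6.2 plans a regression. If the covariates had a correlation of 0.3 to 0.5 with the change (an assumption; the protocol gives no figure), the contrast's detectable d would fall to 0.532 × √(1 − 0.09) = 0.51 or 0.532 × √(1 − 0.25) = 0.46. That is still far from 0.2.

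**The within-group test is well powered for plausible changes.** A reader might infer that the study has little chance of showing a change in high-risk patients. The documents do not support that. The only effect cited has d of about 1.4. With 50 pairs, power is 93% at d=0.5 and 99.8% at d=0.7. At SD 0.27 a non-significant result needs an observed mean reduction below about 0.077, a fifth of the cited 0.38. The protocol does expect a smaller change than that study, but nothing suggests one near d=0.2. This part of the objection stands.

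**Nothing hangs on the sentence.** The target size comes from expected recruitment at 12 centres, the study is observational, and no stop/go criteria apply. This also stands, and it limits the severity.

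**Conclusion.** The subgroup power statement is wrong as written. With the protocol's own inputs, 90% power is reached at d of about 0.47 within the high-risk group and about 0.53 for an unadjusted high versus intermediate comparison. Because no comparator is stated, both readings were checked; neither gives a small effect in the sense of the preceding sentence.

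The practical consequence lies mainly in the contrast between risk groups. If the true difference were d=0.2, it would be missed about 77% of the time (100% − 23%). For the within-group change the overstatement has little effect unless that change is far smaller than the cited one.

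The figures rest on 50 complete pairs, equal SDs and the usual Cohen scale. This should be fixed, but it does not undermine the sample size, the primary analysis or the conduct of the study.

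**What to change.** Replace the subgroup sentence in section 6.1 with:

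> About 50 high-risk patients are expected. If all have paired ratios, this gives 90% power (two-sided alpha 0.05) for a within-group change of d=0.47 and for a high v intermediate difference of d=0.53; the study is underpowered for small effects (d about 0.2) in this subgroup. Subgroup results will be reported as estimates with 95% confidence intervals (expected half-width about 0.08 RV/LV units within the subgroup and 0.09 for the contrast, assuming SD 0.27 in both risk groups).

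It makes sense to correct the neighbouring statement for 200 patients at the same time, since with a two-sided test it has about 80% power at d=0.2, or 90% at d=0.23. The cost is a text edit to one paragraph, with no change to recruitment, data collection or treatment.
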